7.3. Subject Withdrawal Criteria

The following are the criteria for considering withdrawal from the study:

- Withdrawal of patient consent.
- Subject lost to follow-up.
- The subject has a clinically significant adverse event (AE) or serious adverse event (SAE) that would not be consistent with continuation in the study, as determined by the Investigator in discussion with the Medical Monitor.
- Pregnancy.

If a subject withdraws or is withdrawn from the study, the principal reason for withdrawal will be recorded on the electronic case report form (eCRF). If a study subject is discontinued from study medication before the final scheduled visit, all procedures scheduled for that visit should be conducted at the time the subject is discontinued.

8. STUDY TREATMENTS

8.1. Description of Study Medications

8.1.1. Investigational Product

OTX-101 is an aqueous nanomicellar formulation of cyclosporine for topical ophthalmic use. It is supplied in unit dose vials. The subject will self-administer one full drop to both eyes BID. If a full drop is not instilled into the eye, the subject will wait approximately 10-15 seconds and administer a second drop.

8.1.2. Reference Therapy

Not applicable

8.1.3. Rescue Therapy

Subjects are permitted the *ad libitum* use of unpreserved artificial tears

8.2. Randomization and Masking

All subjects will receive OTX-101 0.09%. A supply of study medication from the assigned kit will be dispensed to the subject at the end of the Visit 5a, at Visit 6 (Day 182) and at Visit 7 (Day 273). An additional box of medication will be dispensed at Visit 8 (Day 364) to those subjects who are scheduled to remain in the study until Visit 9 (Day 448).

8.2.1. Unmasking During the Study Period

Not applicable.

8.3. Concomitant Medications

8.3.1. Permitted Medications and Treatments

Therapy considered necessary for the subject's welfare that will not interfere with the evaluation of the study medication may be given at the discretion of the Investigator and in consultation with the Medical Monitor. If there is any question as to whether the medication may interfere, the Investigator should contact the Medical Monitor or Sponsor.

Oral omega-3 fatty acids are permitted if the dosage has been stable for 3 months and the subject stays on the same dose until the end of the study. The subject should not begin oral omega-3 fatty acids during the study. Whenever possible, medications should be administered in dosages that remain constant throughout the study duration. All concomitant medications will be recorded in the eCRF.

Preservative-free artificial tears may be used *ad libitum*.

8.3.2. Prohibited Medications and Treatments

The Medical Monitor should be notified before prohibited medication or therapy is administered, unless the safety of the subject requires immediate action. The decision to administer a prohibited medication or therapy should be done with the safety of the subject as the primary consideration.

Prohibited ocular medications and therapies during the study include any prescription or over-the-counter topical ophthalmic medications other than the assigned study medication (unpreserved artificial tears are permitted) and ocular surgery/ocular laser treatment of any kind.

8.4. Treatment Compliance

Treatment compliance will be monitored by study medication accountability. Throughout the treatment phase, the amount of opened and unopened medication returned at each post-baseline visit will be documented by study site personnel.

8.5. Study Medication Materials and Management

8.5.1. Packaging and Labeling

Study medication will be packaged and labeled at a central packaging facility. Each subject kit will consist of a single Main Box which is to remain at the clinical site.

Each Main Box will contain 3 smaller boxes, each of which contains 210 unit dose vials (105 days supply). The smaller boxes will be sealed and labeled to include the kit number and the visit number at which it is to be dispensed directly to the subjects. Other label information will include patient instructions and safety information.

Clinical sites are to dispense study medication from the kit assigned to the subject at Visit 5a, Visit 6 (Day 182) and Visit 7 (Day 273).

An additional box of medication will be dispensed at Visit 8 (Day 364) to those subjects scheduled to continue treatment until Visit 9 (Day 448). Each box contains 210 unit dose vials (105 days supply).

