
Methodology: This is an open-label extension of OTX-101-2016-001, a randomized, multicenter, double-masked, vehicle-controlled study in which subjects were randomized to 1 of 2 treatment arms and treated for 12 weeks as follows:
 
 • OTX-101 0.09% (N = ■■■ subjects) • Vehicle (N = ■■■ subjects) 
Subjects successfully completing Study OTX-101-2016-001 may be eligible to enroll in this 40 to 52 week open label extension study in which all subjects will receive OTX-101 0.09% therapy. Subjects may also use unpreserved artificial tears, as needed. Subjects assigned to OTX-101 0.09% in Study OTX-101-2016-001 will participate for 40 weeks. Subjects assigned to vehicle in Study OTX-101-2016-001 are eligible to participate for 52 weeks. Both subject sets will total 52 weeks of participation receiving OTX-101 0.09%.
 
Subjects may enroll in Study OTX-101-2016-002 for up to 14 days following completion of Visit 5 of Study OTX-101-2016-001. At Visit 5a, sites will obtain signed informed consent and dispense study medication. If Visit 5a is not conducted on the same day as Visit 5 of Study OTX-101-2016-001, any female subject of childbearing potential must also have a negative urine pregnancy test. Study “Day” approximately reflects the cumulative number of days of exposure to study drug since the baseline visit of Protocol OTX-101-2016-001, regardless of actual calendar time elapsed.
 
Subjects will self-administer study medication topically to both eyes BID for 40 to 52 weeks depending on their treatment assignment in Study OTX-101-2016-001. Safety evaluations for all subjects will be conducted at study visits on Days 182, 273 and 364; the window for Visits 6 (Day 182) and Visit 7 (Day 273) will be ± 7 days; the window for Visit 8 (Day 364) will be +14 days for those subjects assigned to OTX-101 0.09% in Study OTX-101-2016-001. (± 14 days for subjects assigned to vehicle in Study OTX-101-2016-001, participating for 52 weeks in Study OTX-101-2016-002). Subjects assigned to vehicle in Study OTX-101-2016-001, participating for 52 weeks in Study OTX-101-2016-002, will also be evaluated at Visit 9 (Day 448), which will have a visit window of +14 days. Both eyes will be assessed at each visit. Adverse events and concomitant medications will be documented from signing of informed consent to the subject’s final visit.
	

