^f Clinical site personnel will document all received and returned medication at Days 182, 273, 364 and 448. Study medication accountability will be performed by the monitor at each applicable monitoring visit.

^g Examination is required only at the subject’s final visit,

^h Medication is dispensed if the subject is participating for an additional 12 weeks

ⁱ 364 ± 14 days if the subject is participating for an additional 12 weeks

^j Updated ICF due to Amendment #1 to be signed by all participating subjects for Protocol OTX-101-2016-002 Amendment #1

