6. INVESTIGATIONAL PLAN

6.1. Overall Study Design

This will be an extension of OTX-101-2016-001, a randomized, multicenter, double-masked, vehicle-controlled study that enrolled male and female subjects, 18 years of age and older, with a patient-reported history of KCS for a period of at least 6 months, a clinical diagnosis of bilateral KCS supported by OTX-101-2016-001 study assessments, and corrected Snellen VA of better than 20/200 in both eyes at Screening and at Baseline.

Subjects who complete Visit 5 (Day 84) of Study OTX-101-2016-001 may be eligible to enroll in protocol OTX-101-2016-002 within 14 days at the discretion of the Principal Investigator and Sponsor. Subjects who provide written informed consent at Visit 5a and meet the inclusion/exclusion criteria requirements will be enrolled in the study and receive study medication (OTX-101 0.09%). All subjects will participate for at least 40 weeks. Subjects who were randomized to the vehicle arm in Study OTX-101-2016-001 may have the opportunity to participate for additional 12 weeks, total of 52 weeks.

Subjects will self-administer study medication topically to both eyes BID from Visit 5a to Visit 8 (Day 364) or Visit 9 (Day 448). Safety evaluations will be conducted at all study visits. The window for Visits 6 and 7 will be ± 7 days. The window for Visit 8 will be +14 days for those subjects assigned to OTX-101 0.09% in Study OTX-101-2016-001 (± 14 days for subjects assigned to vehicle in Study OTX-101-2016-001, participating for 52 weeks in Study OTX-101-2016-002), and Visit 9 will be +14 days. Both eyes will be assessed at each visit. Adverse events and concomitant medications will be documented from signing of informed consent at each study visit.

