8.5.2.2. Administration

Subjects will self-administer study medication topically to both eyes BID for 40 or 52 weeks. The subject should be in a seated position and should tilt his or her head backward for

administration of the study medication. The vial of study medication should be held at an almost vertical position above the eye while the lower eyelid is pulled down gently, and one full drop is placed into the conjunctival cul-de-sac of each eye from the same vial. (Note: if a full drop is not instilled into the eye, the subject should wait approximately 10-15 seconds and administer a second drop.) The tip of the vial should not touch the eye. After instilling a drop in each eye, the remaining contents of the vial should be emptied and the vial should be stored in the foil pouch and placed back in the box.

Twice each day, approximately 12 hours apart, the subject will open a new unit dose vial and administer 1 full drop to each eye, store the used vial in the foil pouch, and place it back in the box for return to the clinical site. At each post-baseline visit, the box, complete with used vials/pouches and any unopened study medication will be returned to the clinical site where the used and unopened medication will be documented and the next designated box will be dispensed to the subject.

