10.2. Treatment Visits

10.2.1. Visit 6 (Day 182), Visit 7 (Day 273) and Visit 8 (Day 364)*

Procedures performed on Days 128 (± 7 days), 273 (± 7 days) and 364* (± 14 days) will include the following:

- AE assessment
- Concomitant medication review
- Urine pregnancy test (women of childbearing potential only)
- Corrected Snellen VA
- Slit lamp examination
- IOP
- Collect and document used and unopened study medication materials
- Dispense study medication

* If not the final visit

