10.3. Final Study Visit: Visit 8 (Day 364) or Visit 9 (Day 448)

Procedures performed at the subject's final visit; i.e., Day 364 (+14 days) or Day 448 (+14 days), depending on their treatment assignment in Study OTX-101-2016-001, will include the following:

- Collect and document used and unopened study medication materials
- AE assessment
- Concomitant medication review
- Urine pregnancy test (women of childbearing potential only)
- Corrected Snellen VA
- Slit lamp examination
- IOP
- Ophthalmoscopy/dilated fundus examination

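### The 105-day Visit 7 box does not cover the longest in-window Visit 7 to Visit 8 interval (112 days), so a near-perfectly adherent former vehicle subject can be without drug for 1 to 7 days

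*Protocol*

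**What the plan says.** **Supply.** Protocol 8.5.1: "Each Main Box will contain 3 smaller boxes, each of which contains 210 unit dose vials (105 days supply". One box is handed out at each of Visits 5a, 6 and 7, and one more at Visit 8 for those going on to Visit 9. Protocol 8.5.2.2 has the subject open a new vial twice a day, one vial serving both eyes.

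**Return of leftovers.** Under 8.5.2.2, at each post-baseline visit "any unopened study medication will be returned to the clinical site". Section 8.5.2.3 has the site seal the returned kit into the Main Box before giving out the next one. No resupply between visits is described, and the telephone contacts in 10.4 cover only adverse events and concomitant medication.

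**Windows.** Visit 7 is Day 273 ± 7. For former vehicle subjects who continue, Table 2 footnote i sets Visit 8 at "364 ± 14 days if the subject is participating for an additional 12 weeks", and section 10.2.1 agrees: "273 (± 7 days) and 364* (± 14 days". For final visits, section 10.3 gives "Day 364 (+14 days) or Day 448 (+14 days".

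**End of dosing.** The Synopsis says "topically to both eyes BID for 40 to 52 weeks depending on their treatment assignment in Study OTX-101-2016-001" and section 8.5.2.2 says "Subjects will self-administer study medication topically to both eyes BID for 40 or 52 weeks". Section 6.1 says "topically to both eyes BID from Visit 5a to Visit 8 (Day 364) or Visit 9 (Day 448".

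**Analysis.** SAP 7.5 takes exposure as the span from first to last dosing date, counting both days, and summarises compliance as below 70% or at least 70%.

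**The concern.** The visit windows and the supply rules were set separately, and each is measured from the nominal day, not from the actual previous visit. If Visit 7 is early and Visit 8 late, one box has to last longer than it can. The subject has followed the protocol and still has no drug.

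For a former vehicle subject this falls in the middle of the planned 52 weeks. Visual acuity, slit lamp and intraocular pressure at Visit 8 are then taken after several days off drug. The study's only purpose is long-term safety, and the One Year Safety Population in Protocol 11.5.1.1 is defined by total exposure to active drug, so a forced interruption that the exposure formula counts as treatment deserves attention. Adverse events are collected throughout in any case.

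**Working it through.** **Plan's own figure.** 210 vials / 2 per day = 105 days. It reproduces.

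**Windows (study day).** Visit 5a: 84. Visit 6: 182 ± 7 = 175 to 189. Visit 7: 273 ± 7 = 266 to 280. Visit 8, former vehicle continuing: 364 ± 14 = 350 to 378. Visit 8, former OTX-101 (final): 364 to 378. Visit 9: 448 to 462.

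**Longest permitted interval (latest next visit minus earliest dispensing visit).**

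| Interval | Subjects | Longest, days | Beyond 105 |
|---|---|---|---|
| 5a to 6 | all | 189 − 84 = 105 | 0 |
| 6 to 7 | all | 280 − 175 = 105 | 0 |
| 7 to 8 | former vehicle, continuing | 378 − 266 = 112 | 7 |
| 7 to 8 | former OTX-101 (final) | 378 − 266 = 112 | 7, only if dosing runs to the visit |
| 8 to 9 | former vehicle (final) | 462 − 350 = 112 | 7, only if dosing runs to the visit |

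The Table 2 row of days since Visit 5a gives the same result: (280 + 14) − (189 − 7) = 112. A delayed Visit 5a therefore does not change it.

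**Which rows matter.** If dosing stops at 40 or 52 weeks (Day 364 or 448), the last box has to cover at most 364 − 266 = 98 or 448 − 350 = 98 days, so the last two rows show no gap. The former vehicle Visit 7 to 8 row falls in mid-treatment and holds under either rule for the end of dosing.

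**How many date pairs.** 15 Visit 7 days × 29 Visit 8 days = 435. A gap needs an interval of at least 106 days, so Visit 7 on Days 266 to 272 and Visit 8 on Days 372 to 378. Gaps of 1, 2, 3, 4, 5, 6 and 7 days occur in 7, 6, 5, 4, 3, 2 and 1 pairs: 28 pairs in all, with mean 84/28 = 3 days.

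**Margin at nominal days.** 364 − 273 = 91 days, and 105 − 91 = 14 days to spare.

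**Adherence needed.** 112 days × 2 = 224 doses against 210 vials. Missing 14 doses (210/224 = 93.75% adherence) removes the 7-day gap. A 1-day gap (106 days, 212 doses) disappears if 2 doses are missed.

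**Visibility in SAP 7.5.** If compliance is doses taken over doses scheduled (the SAP gives no formula), 7 days off in 364 is 357/364 = 98.1%, well inside the upper category.

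**Effect on the category of at least 360 days.** Take the first dose on Day 84. If the last dose is on Day 448, the formula gives 365 days, so a gap of at least 6 days is needed to bring dosed days below 360: 2 + 1 = 3 of 435 pairs. If the last dose is on Day 447 (364 days), a gap of at least 5 is needed: 3 + 2 + 1 = 6 of 435.

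**Would leftover Visit 6 vials be enough?** The least left at Visit 7, with Visit 6 on Day 175, is 105 − (V7 − 175) = 280 − V7 days. The largest gap, with Visit 8 on Day 378, is 378 − V7 − 105 = 273 − V7 days. The difference is always at least 7 days.

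**The case against.** The strongest reply is that nothing printed is wrong and the combination is rare. The gap needs a former vehicle subject who continues, an early Visit 7, Visit 8 in the last 7 days of its window, and almost no missed doses. All of that stands, and it limits the weight of the point.

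It is also fair that the gap is not hidden. Sites document used and unopened vials at each post-baseline visit (Protocol 8.4, 8.5.3), and the SAP plans Listing 16.2.5 on dosing days and compliance. An empty box after more than 105 days can be seen there. Only the SAP 7.5 summaries miss it.

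The analysis is descriptive, with no hypothesis test, and nothing in the documents shows that 1 to 7 days off drug changes the Visit 8 findings. The exposure formula ignores interruptions of every kind, so correcting for supply gaps alone would be inconsistent.

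The two rules for the end of dosing agree nominally: (364 − 84)/7 = 40 weeks and (448 − 84)/7 = 52 weeks. They part only when a final visit is late.

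None of this supplies the missing drug. As written, the rules cannot deliver continuous twice-daily dosing to a fully adherent subject who keeps to every window.

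**Conclusion.** The point holds as a small mismatch between supply and visit windows, worth correcting because correction is nearly free. It affects former vehicle subjects continuing to Visit 9, between Visits 7 and 8, for 1 to 7 days.

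Four stronger readings are tempting, and the documents do not support them:

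- That the 105-day figure is an error. It is correct.
- That 28 of 435 (6.4%) estimates how often this happens. It counts permitted dates, ignores missed doses, and says nothing about how visits are actually scheduled.
- That every subject's last box falls short. That follows only if dosing is meant to run to the final visit, and the shortfall would then come after the planned 40 or 52 weeks.
- That the gap is undetectable or undermines the safety results. Accountability data can show it, adverse events are still collected, and the effect on the 12-month exposure category is negligible.

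The conclusion assumes two vials per day from visit to visit, no extra vial for a repeated drop (the protocol does not call for one), and no resupply outside the written procedures. Study days are themselves described as approximate.

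**What to change.** Choose one of two for former vehicle subjects continuing to Visit 9.

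(a) Let them keep unopened Visit 6 vials until the Visit 7 box is used up. This always covers the Visit 7 to 8 gap, with at least 7 days to spare. Amend Protocol 8.5.2.1, 8.5.2.2, 8.5.2.3 and 8.5.3 together, since all bear on returning unopened medication, and give the collection item in 10.2.1 the same exception. Cost: slightly more complex accountability.

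(b) Require Visit 8 within its present window and no later than 105 days after the actual Visit 7 date. The cap never falls before 266 + 105 = Day 371. Amend the Synopsis (Methodology), sections 6.1 and 10.2.1, Table 2 with footnote i, and SAP 2.2 and its Table 1, so that no schedule contradicts another. Cost: a slightly narrower Visit 8 window.

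Neither option needs extra drug. State once whether dosing stops at 40 or 52 weeks or runs to the final visit. Only in the second case do the final visits need a similar cap.

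The estimated completion date was September 2017, and the SAP already reports 258 enrolled and a data cutoff of 12 May 2017. If dispensing is complete, only the analysis can change: SAP 7.5 should report exposure net of all documented interruptions, whatever their cause. The accountability sections describe vial counts per visit and not run-out dates, so this may take more than a line of programming.

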8.5.2. Storage, Administration, and Dispensing

8.5.2.1. Storage

Study medication must be stored as indicated on the package label: “Store at [REDACTED] ([REDACTED])” in a secured area. A temperature log will be maintained at each clinical site. Subjects should be instructed to store study medication at home at room temperature. After opening a pouch, the remaining vials should be stored in the pouch until used. Subjects will retain all opened and unopened study medication materials (unit dose vials, foil pouches, boxes) to return to the site.

8.5.2.2. Administration

Subjects will self-administer study medication topically to both eyes BID for 40 or 52 weeks. The subject should be in a seated position and should tilt his or her head backward for

administration of the study medication. The vial of study medication should be held at an almost vertical position above the eye while the lower eyelid is pulled down gently, and one full drop is placed into the conjunctival cul-de-sac of each eye from the same vial. (Note: if a full drop is not instilled into the eye, the subject should wait approximately 10-15 seconds and administer a second drop.) The tip of the vial should not touch the eye. After instilling a drop in each eye, the remaining contents of the vial should be emptied and the vial should be stored in the foil pouch and placed back in the box.

Twice each day, approximately 12 hours apart, the subject will open a new unit dose vial and administer 1 full drop to each eye, store the used vial in the foil pouch, and place it back in the box for return to the clinical site. At each post-baseline visit, the box, complete with used vials/pouches and any unopened study medication will be returned to the clinical site where the used and unopened medication will be documented and the next designated box will be dispensed to the subject.

8.5.2.3. Dispensing

At Visit 5a, the kit labeled with that visit will be removed from the Main Box at the site and dispensed to the subject with instructions to return the box along with used and unused study medication at Visit 6. The two remaining kits will remain in the Main Box at the site.

At Visit 6 (Day 182), the kit returned by the subject will be taken by the site, sealed, and placed back into the Main Box and the site will dispense the kit labeled Visit 6 to the subject with instructions to return the box along with used and unused study medication at Visit 7.

At Visit 7 (Day 273), the kit returned by the subject will be taken by the site, sealed, and placed back into the Main Box and the site will dispense the kit labeled Visit 7 to the patient with instructions to return the box along with used and unused study medication at Visit 8.

At Visit 8 (Day 364), the kit returned by the subject will be taken by the site, sealed, and placed back into the Main Box ready for the CRA to perform drug accountability and reconciliation. An additional box of drug will be dispensed to those subjects scheduled to continue treatment until Visit 9 (Day 448).

At Visit 9 (Day 448), the box returned by the subject will be taken by the site, sealed and retained for the CRA to perform drug accountability and reconciliation.

After site close out, the site or CRA will ship all materials back to the supplier.

8.5.3. Study Medication Accountability

The Investigator or designee (e.g., study coordinator or pharmacist) will maintain a full accountability record for the study medication and will be responsible for recording the receipt, dispensing, and return of all supplies of the study medication using the inventories supplied by the Sponsor. Clinical site personnel will document all received and returned study medication at each post-baseline visit. Study drug accountability will be conducted by the monitor at each applicable monitoring visit.

As described in Section [REDACTED] the subject will return all opened vials/pouches as well as any unopened study medication at each post-baseline visit. The monitor will review dispensing and

drug accountability records during site visits and at the completion of the study and note any discrepancies.

All investigational study medication must be stored in a secure facility, with access limited to the Investigator and authorized staff.

